13.1 Analysis software

All analyses will be conducted in Stata v18 (StataCorp, 2023), or later (to be confirmed in final report).

13.2 Analysis principles and populations

Analyses will follow the principles of intention-to-treat (ITT) with participant's outcomes analysed according to their original, randomised group, where data are available, irrespective of deviations FLARE Statistical Analysis Plan Version 1.0

based on non-compliance. One-sided 97.5% confidence limits (equivalent to the upper bound of the two-sided 95% confidence interval) will be reported for the primary analysis. There will be no predefined non-inferiority margins for the remaining secondary outcomes, these will be compared for evidence of superiority and two-sided tests at the 5% significance level will be used.

13.3 Screening, eligibility, recruitment and follow-up data

This trial will be reported according to the CONSORT guidelines for a parallel group RCT (Schulz et al., 2010). The flow of participants through each stage of the trial will be presented in a CONSORT diagram (see **Appendix A** for an example).

The number of individuals screened, eligible, consented, and randomised will be presented. Reasons for ineligibility (before and during surgery) and non-consent will be provided, where available.

The number of sites recruited and patient recruitment by site will be summarised. The average recruitment rate per month, and per site per month, will be presented. Recruitment graphs presenting the overall recruitment by month and the actual vs target recruitment will be produced.

Response rates to the clinician and participant reported completed questionnaires will be presented by treatment arm, and overall, at each follow-up timepoint (one week, six-weeks, three-months and six months).

The type (from the trial or from follow-up) and timing of withdrawals will be presented by randomised group, and overall, with reasons for withdrawal where available.

13.4 Baseline data

All baseline data will be summarised descriptively by treatment group, as randomised and as included in the primary analysis. The baseline demographics, clinical characteristics and treatment preference of the participant will be reported. No formal statistical comparisons for baseline imbalance will be undertaken, but any noteworthy difference will be descriptively reported. Continuous data will be presenting using a mean and standard deviation and categorical data will be present using a count and a percentage.

A separate table of patients who consented but were not randomised will also be presented.

13.5 Primary analysis

The primary outcome measure (PEM Hand Health Profile) will be reported descriptively, by trial arm and overall, for all data collection timepoints (baseline, six-weeks, three-months and six-months postrandomisation).

The primary analysis will compare PEM Hand Health Profile scores between treatment groups using a covariance pattern mixed effect linear model, incorporating data from all post-randomisation time points (six-weeks, three-months and six-months). The model will adjust for digital nerve injury, anaesthetic type, baseline PEM Hand Health Profile score (both pre and post-injury), time, treatment arm, treatment-by-time interaction as fixed effects, with site and participant as random effects to account for clustering by site and repeated observations per participant.

The correlation of observations within participants over time will be modelled by a covariance structure. The different covariance structures for repeated measurements that are available as part of the analysis software will be applied to the model. The Akaike information criterion will be used to compare models specifying different covariance structures with smaller values preferred. Model assumptions will be checked as follows: the normality of the standardised residuals will be assessed using a QQ plot, and homoscedasticity will be assessed by means of a scatter plot of the standardised residuals against fitted values. One possible violation of the assumptions may be the normality of the residuals due to a potential ceiling or floor effect where a lot of patients have a score of zero. In this instance, we will carry out an additional sensitivity analysis using a semi-parametric approach based on an ordinal regression model using the 'glm' Stata command with a logit link function.

Participants will only be included in the model if they have complete data for the baseline covariates and a valid PEM Hand Health Profile score for at least one post-randomisation timepoint.

The treatment effect at all time points (six-weeks, three-months and six-months) and overall will be extracted in the form of an adjusted mean difference, two-sided 95% CIs (equivalent to a one-sided 97.5% CI) and p-value. The primary timepoint of interest is six-months post-randomisation. A detailed description of how we will interpret the treatment effect estimate is included in Appendix A.

Analysis of the primary outcome will be checked by a second statistician according to YTU SOPs and Guidance and a copy of F16: Primary Analysis Sign Off Form will be completed, signed and stored in the Trial Master File.

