5.5.2 Determination of Sample Size

There will be a 22-month recruitment period for the FLARE trial. The total target sample size will be 310 participants.

A six-point difference on the Patient Evaluation Measure (PEM) represents the threshold at which treatment differences become important (based on observational data from patients with Dupuytren's contracture for the DISC trial (HTA 15/102/04)). However, recent analysis within a flexor tendon population has found a seven-point difference on the PEM to be important and thus represents an appropriate non-inferiority margin to be used in this population. For 90% power and alpha=0.025, 310 participants are required to establish noninferiority within a margin of 7 points on the PEM (SD=17; upper 80% confidence limit (22)), based on the lower limit of a 95% two-sided confidence interval (equivalent to a one-sided 97.5% CI) and 20% attrition.

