8.2 Data collected via paper

Participants will be given the option to complete consent forms, baseline, and follow-up postal questionnaires on paper, if required. Paper consent forms and baseline questionnaires will be returned to sites to be recorded into the REDCap study management system. Paper follow-up questionnaires will be returned to YTU where data will be transferred into the REDCap study management system. Paper copies will be stored in a locked filing cabinet in a room with restricted access at the University of York.

9. Sample Size

A six-point difference on the PEM represents the threshold at which treatment differences become important (based on observational data from patients with Dupuytren's contracture for the DISC trial (HTA 15/102/04)). However, recent analysis within a flexor tendon population has found a seven-point difference on the PEM to be important and thus represents an appropriate non-inferiority margin to be used in this population. For 90% power and alpha=0.025, 310 participants are required to establish noninferiority within a margin of seven points on the PEM (SD=17; upper 80% confidence limit), based on the lower limit of a 95% two-sided confidence interval (equivalent to a one-sided 97.5% CI) and 20% attrition.

10. Randomisation

Eligible patients will be randomly allocated in a 1:1 ratio to receive either repair of both FDS and FDP or repair of FDP only using block randomisation stratified by study site with randomly varying block sizes. An independent statistician at YTU, who is not involved in the recruitment of participants, will generate the allocation schedule. The allocation schedule will be generated in Stata v17 or later.

Randomisation will be carried out using REDCap and be completed in theatre with treatment allocated on an individual patient basis.

11. Blinding

Patients will be blinded to treatment allocation and will not be told which type of tendon repair they have received. The resulting scar will not disclose the allocated intervention. A code break procedure for clinical care or safety reporting will be in place.

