13.6 Analysis of secondary outcomes

All outcomes will be reported descriptively for all data collection timepoints.

The PEM Hand Health Profile subscale will be extracted from the primary analysis model at six-weeks and three-months post-randomisation.

Continuous outcome measures will be analysed in a similar way to the primary outcome, swapping baseline PEM Hand Health Profile score with the baseline value of the outcome as a covariate. If the measure was not completed at baseline (PEM treatment subscale, PEM Overall assessment, ROM and Grip strength) no adjustment will be made.

Adherence to the splint regimen at six-weeks post-randomisation will be summarised descriptively, by trial arm and overall, using counts and percentages for items one to four, and a mean and standard deviation for item five.

Adherence to the therapy regimen at six-weeks and three-months post-randomisation will be summarised descriptively, by trial arm and overall, using counts and percentages.

Treatment and outcome satisfaction will be analysed descriptively.

Complications (including deep wound infection (Yes/No), tendon rupture (Y/N), superficial infection (Yes/No) and rehospitalisation (Yes/No)) and further surgical procedures (Y/N) will be analysed using

a separate logistic regression models including similar covariates as the primary analysis model providing there are a minimum number of events (at least 5 per arm).

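### The primary model gives each baseline PEM score one slope for all three visits; if the baseline relation changes over time, the 6-month comparison is unbiased but somewhat less precise than it could be

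*SAP*

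**What the plan says.** SAP section 13.5 specifies a covariance pattern mixed model for the PEM Hand Health Profile, "incorporating data from all post-randomisation time points (six-weeks, three-months and six-months". The listed terms include "baseline PEM Hand Health Profile score (both pre and post-injury), time, treatment arm, treatment-by-time interaction as fixed effects". Nothing lets a baseline slope vary by visit. Protocol section 5.5.4 has the same structure, with treatment-by-time as the only interaction. The residual covariance is not fixed in advance; it is chosen by AIC. Six months is the primary time point.

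SAP section 13.6 carries the form to other outcomes: "Continuous outcome measures will be analysed in a similar way to the primary outcome, swapping baseline PEM Hand Health Profile score" for the outcome's own baseline value. In practice this reaches PRWHE, because the other continuous outcomes listed there have no baseline measure.

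For the sample size (SAP section 9), "For 90% power and alpha=0.025, 310 participants are required", with a "margin of seven points on the PEM (SD=17; upper 80% confidence limit").

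**The concern.** The post-injury baseline PEM is taken between injury and surgery, so it describes an acutely injured, unrepaired finger. Protocol section 4.7 has the splint worn for the first four to six weeks, and section 1.2 puts rehabilitation at 12 weeks or more. It is plausible that this score relates differently to PEM at 6 weeks, when the splint is just coming off, than to PEM at 6 months. The argument is weaker for the pre-injury score.

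If the relation does change, a single slope is a compromise between visits and is not the best adjustment at 6 months. The confidence limit at 6 months decides non-inferiority, so the question is how much wider that interval becomes. The planned diagnostics would not show the problem. AIC is used only to choose the covariance structure, and the QQ plot and the residual-versus-fitted plot do not test whether slopes are equal over time.

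**Working it through.** **Inputs from the documents.** Margin 7, SD 17, 90% power, one-sided alpha 0.025 and 20% attrition (SAP section 9); "Eligible patients will be randomly allocated in a 1:1 ratio" (SAP section 10); three post-randomisation visits (SAP section 13.5).

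**Inputs assumed.** The correlation of baseline PEM with PEM at 6 weeks, 3 months and 6 months; inter-visit correlation 0.5 to 0.7, exchangeable or AR(1); equal SD at each visit; one standardised covariate standing for the two PEM scores; no site effect.

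**Step 1: the plan's own figure.** n per arm = 2 × (1.960 + 1.282)² × 17² / 7² = 123.9, so 124 per arm and 248 in total. Then 248 / 0.8 = 310, an exact match. The protocol's wording, "margin of 7 points on the PEM (SD=17; upper 80% confidence limit (22"), also mentions 22, but an SD of 22 gives 208 per arm and 520 in total, so 17 was used. The calculation takes no credit for baseline adjustment. Unadjusted power with 124 per arm is 90.0%.

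**Step 2: variance at 6 months.** Let r be the vector of the three baseline correlations, r6 its 6-month element, and W the residual correlation matrix.
- Visit-specific slopes: variance factor 1 − r6².
- Common slope b: variance factor 1 − r6² + (r6 − b)², where b = 1′W⁻¹r / 1′W⁻¹1.
- SE = 17 × √(2/124 × factor); power = Φ(7/SE − 1.96) for a true difference of zero.

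**Step 3: one case in full.** Take r = 0.5/0.3/0.1 with exchangeable inter-visit correlation 0.6 and an unstructured residual covariance. The visit weights are 0.52, 0.33 and 0.15, and b = 0.375. The common-slope factor is 0.99 + (0.1 − 0.375)² = 1.066, against 0.99 with visit-specific slopes: ratio 1.076. The SE is 2.229 against 2.148, and power 88.1% against 90.3%.

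**Step 4: the range.** The lower end of each excess is an equally weighted slope, as an exchangeable fitted structure gives. The upper end is an unstructured fit.

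| Baseline correlation (6 wk/3 mo/6 mo) | Common slope b | Excess 6-month variance | Power, common slope | Power, visit-specific |
|---|---|---|---|---|
| 0.3/0.3/0.3 | 0.300 | 0% | 92.5% | 92.5% |
| 0.4/0.3/0.2 | 0.300–0.321 | 1.0–1.5% | 90.7–90.9% | 91.1% |
| 0.3/0.2/0.0 | 0.167–0.197 | 2.8–3.9% | 88.9–89.2% | 90.0% |
| 0.5/0.3/0.1 | 0.300–0.409 | 4.0–9.7% | 87.5–89.2% | 90.3% |

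In the three decaying rows the 6-month visit has weight 0.06 to 0.37 in the common slope.

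**Step 5: when adjustment does harm.** The common-slope model is worse than no baseline adjustment when 1 − r6² + (r6 − b)² > 1. For positive b, that means b > 2 × r6. At 0.4/0.3/0.2, b is about 0.32, below 0.40, so adjustment still helps. At 0.3/0.2/0.0 and 0.5/0.3/0.1 it does not.

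**Step 6: simulation.** With 155 per arm, 20% monotone dropout and 1,500 runs per scenario, the ratio of the 6-month SEs (common to visit-specific) was 1.008 for 0.4/0.3/0.2 and 1.034 for 0.5/0.3/0.1. Bias was at most 0.04 points in every scenario run.

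**The case against.** The strongest reply is that a common slope is prespecified, valid and unbiased under randomisation, and that no loss can be shown from the documents. They report no correlation between baseline PEM and PEM at any visit and none between visits, and the covariance structure is left to AIC. The steep case alone moves from 4% to nearly 10% depending on those unseen inputs. All of this stands, and it is why the size can only be given as a conditional range that includes zero.

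The sample size also takes no credit for baseline adjustment, so under mild decay the written model still exceeds its 90% design power. That stands too. Under steeper decay it falls slightly short.

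Finally, the CACE analysis in SAP section 13.7.1 regresses the 6-month score alone on baseline, so it already has a 6-month slope of its own. That is true, but it is a sensitivity analysis with a different estimand and does not repair the primary model.

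A reader might infer more: that the early visits fix the adjustment, that 6-month precision is certainly lost, or that the non-inferiority conclusion is at risk. The documents do not support this. The slope is a weighted mean that includes 6 months, the loss depends on slopes that differ, and there is no bias.

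**Conclusion.** The structural point holds: as written, each baseline PEM score has one slope across three visits. The consequence is limited to precision at 6 months and depends on slopes that change over time, which is plausible for the post-injury score but not quantified in either document. Over the assumed range the excess variance runs from 0% to about 10%, or about 0 to 3 points of power. A collapse from 0.6 to 0 would cost more (SE 9 to 14% higher), but nothing in the documents points to so extreme a pattern. The result rests on one covariate standing for two, equal SDs and no site effect. This is a minor efficiency refinement, not an error in the analysis. For PRWHE it matters less still, because that outcome is secondary and has no margin.

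**What to change.** In SAP section 13.5, add time-by-baseline interactions for the pre-injury and the post-injury PEM Hand Health Profile scores. In section 13.6, state the same for baseline PRWHE. Record the change in the SAP amendment log before outcome data are seen by arm. The treatment contrast, margin and analysis population do not change.

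The cost in the primary model is four coefficients: two scores × (3 − 1) visits. For PRWHE it is two for each baseline score that enters. If the slopes are in fact equal, the loss is negligible: estimating a slope from the 6-month visit alone adds variance of order 1/248, about 0.4% per score, and the pooled slope already incurs most of that.

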7.1 Primary outcome

The primary outcome measure is the Patient Evaluation Measure (PEM) Hand Health Profile completed at baseline, six-weeks, three-months and six-months post-randomisation. The pre-specified primary timepoint of interest is six-months post-randomisation.

The PEM is widely used in National Institute for Health and Care Research (NIHR) funded hand trauma studies and is the main patient reported outcome measure (PROM) used for flexor tendon injuries in the British Society for Surgery of the Hand (BSSH) United Kingdom National Hand Registry. The PEM comprises 19 items and three subscales; Treatment (5-items); Hand Health Profile (11-items) and Overall assessment (3-items). The 11-items which make up the Hand Health Profile subscale will be the primary outcome measure for the FLARE trial.

Items on the PEM Hand Health Profile subscale are measured on seven-point Likert scale such as 1 = Never and 7 = All the time, for example, with questions relating to symptoms, satisfaction and general disability. Scores across the 11-items are summed and used to generate a 0%-100% score to determine an overall disability score, with higher scores indicating greater levels of disability. At baseline the PEM will be collected twice: the first determining the patients Hand Health Profile before they sustained their injury and the second after their injury occurred.

The 11-item PEM Hand Health Profile will not be scored if more than two items are missing. If up to two items are missing, the missing items will be replaced with the mean of the remaining non-missing items.

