17.1 Appendix A Accepting non-inferiority

Section 13.5 outlines how we will determine whether repair of FDP only is non-inferior to repair of both FDS and FDP. The primary endpoint is the PEM score at six months. The desired direction of effect is an increase in PEM scores (higher PEM scores are more favourable). When modelling the treatment effect, the treatment allocations will be coded as 1= intervention (repair of FDP only) and 0= control (repair of both FDS and FDP). Therefore, a positive effect will mean the treatment difference will be positive. The non-inferiority margin has been specified as six points and non-inferiority will be accepted if the lower bound of the of the one-sided 97.5% confidence interval for the treatment difference at six months is greater than the non-inferiority margin of -7 points (a 7-point reduction). Figure 1 shows how we will interpret different possible results.

Figure 1: Example scenarios of non-inferiority in the FLARE trial

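### The SAP's sensitivity analysis for floor or ceiling effects names two incompatible models, and nothing links its result to the 7-point margin

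*SAP*

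**What the plan says.** The primary outcome is the PEM Hand Health Profile. SAP section 7.1: "Scores across the 11-items are summed and used to generate a 0%-100% score", with higher scores meaning more disability. SAP section 13.5 fits a covariance pattern mixed linear model to the three follow-up times, "with site and participant as random effects to account for clustering by site and repeated observations per participant". The effect is reported as an "adjusted mean difference, two-sided 95% CIs (equivalent to a one-sided 97.5% CI) and p-value", with six months as the primary time point. SAP Appendix A (17.1) accepts non-inferiority if the confidence bound for that difference "is greater than the non-inferiority margin of -7 points (a 7-point reduction").

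Section 13.5 checks residuals with a QQ plot and a residual-versus-fitted plot. It names one possible violation, a "potential ceiling or floor effect where a lot of patients have a score of zero". In that case, "we will carry out an additional sensitivity analysis using a semi-parametric approach", described as an "ordinal regression model using the 'glm' Stata command with a logit link function".

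The SAP does not state the distribution family, any rescaling or grouping of the score, the time points used, the handling of participant and site, the effect measure, or how the result bears on non-inferiority. Section 13.7 covers only the CACE and missing-data analyses, and the shell for the primary result (Table 18) has a mean-difference column only.

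**The concern.** The specification contradicts itself. An ordinal regression models the probability of being at or below each level of the score, with a cut-point for each boundary. A GLM with a logit link models a single mean that must lie between 0 and 1. On a 0-100 score the stated command needs a rescaling, after which it is a binomial or fractional-logit model for the mean, not an ordinal one.

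Three things follow.

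- Two analysts could follow the sentence in good faith and fit different models. The choice would then be made with the data in hand, which pre-specification is meant to prevent.
- `glm` has no random effects, so the participant and site structure of the primary model is dropped unless something replaces it. The SAP does not say what would.
- The natural output of either model is an odds ratio, while the trial is judged on a difference in PEM points. The check for the one violation the SAP names therefore has no stated way to support or question the conclusion.

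**Working it through.** **1. The plan's own figure.** SAP section 9: "For 90% power and alpha=0.025, 310 participants are required to establish noninferiority within a margin of seven points on the PEM", with SD 17 and 20% attrition.

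n per arm = 2 × (1.960 + 1.282)² × 17² / 7² = 2 × 10.507 × 289 / 49 = 123.9, so 124. Total 248, and 248 / 0.80 = 310. The figure reproduces, and it rests wholly on a mean difference in PEM points.

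**2. The two models named.**

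- Logit-link GLM, Y = PEM/100: logit E(Y) = β₀ + β₁·arm. Two parameters.
- Cumulative logit with K levels: logit P(Y ≤ k) = αₖ − β·arm, for k = 1 to K − 1. That is K − 1 cut-points plus the arm effect.

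Eleven items scored 1 to 7 give sums from 11 to 77, hence 67 possible totals when all items are complete.

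Both models were fitted to the same simulated data. Assumptions, none of them in the documents: normal latent score with SD 20 and control mean 5, 15 or 25; values cut at 0 and 100 and rounded to a 67-level grid; 10,000 per arm; arm shift set to give a true mean difference of 7; higher PEM taken as worse. The ordinal model used 8 grouped levels, so 8 parameters against 2.

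| Control scores at zero | Control mean | Raw difference (points) | GLM odds ratio | Ordinal odds ratio |
|---|---|---|---|---|
| 42% | 10.6 | 7.25 | 1.83 | 2.39 |
| 23% | 17.8 | 6.55 | 1.49 | 1.93 |
| 12% | 26.0 | 6.86 | 1.39 | 1.86 |

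The two are not interchangeable.

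**3. Is there one odds ratio for 7 points?** On the mean scale, with control mean m (assumed), OR = [(m+7)/(93−m)] / [m/(100−m)].

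| m | 5 | 10 | 20 | 30 | 40 |
|---|---|---|---|---|---|
| OR for +7 | 2.59 | 1.84 | 1.48 | 1.37 | 1.33 |

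For example, at m = 10: (17/83) / (10/90) = 1.84. No fixed odds ratio can stand in for the margin.

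**4. Can the result be returned to points?** Yes. From the GLM, difference = 100 × [expit(β₀ + β₁) − expit(β₀)]. In the three data sets this gave 7.25, 6.55 and 6.86 points, equal to the raw differences. With only an arm term that equality is built in, so it shows that a conversion exists, not that the model is robust. An ordinal fit can likewise be turned into model-based means. The SAP specifies neither step.

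**5. How exposed is the primary test?** Under the same three settings with 124 per arm, an unadjusted mean-difference test (unequal variances, 4,000 runs each) was run at a true difference of 7. It wrongly declared non-inferiority in 0.0278, 0.0285 and 0.0268 of runs, against 0.025 nominal. The simulation standard error is √(0.025 × 0.975 / 4,000) = 0.0025, so each is within about 1.4 standard errors of nominal.

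**6. The margin itself.** Appendix A treats higher PEM as better and uses a lower bound against −7. Section 7.1 treats higher as worse, and section 13.2 refers to the upper bound. Appendix A also gives the margin as six points in the same sentence as −7, while section 9 uses seven.

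**The case against.** The strongest defence is that this is a labelling slip. A quasi-likelihood logit model for the mean of a bounded score is a sensible response to many zeros, fits the SAP's description of a semi-parametric approach, and converts to PEM points (step 4). If that is what was meant, only the word ordinal is wrong. This is plausible, but the SAP does not say so, and a statistician who took ordinal literally would fit a different model. A cumulative-logit model could also be assembled in `glm` by stacking a binary indicator for each threshold, but the SAP describes no such construction.

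The SAP's silence on repeated measures is not proof of an error. A six-month-only model needs no participant term, and `glm` accepts cluster-robust standard errors. SAP section 13.7.1 already uses that pattern for the CACE analysis. That objection stands: what is shown is that `glm` cannot carry the primary model's random effects and that no substitute is stated.

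A reader might go further and infer that this model replaces the primary analysis. Section 13.5 says it is additional and conditional, so the decision stays with the linear model. A reader might also infer that the check could never be judged against 7 points, or that it is worthless. Step 4 rules out the first, and a direction of effect could be read from either model, which rules out the second. Nor is the primary result left unexamined: two residual plots are pre-specified.

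**Conclusion.** Wrong as written, of low to moderate severity. The sentence joins two models that are not the same, leaves out the family and scaling needed to run the one named by the command, and gives no effect measure or rule tying the result to the 7-point margin. The incompatibility follows from the form of the models and needs no assumption. The size of the disagreement (for example 1.83 v 2.39) depends on the assumed score distributions and the grouping into 8 levels.

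The sample size, primary test and decision rule are untouched. The documents give no expected proportion of zero scores, so whether the check will be triggered is unknown; the trigger is a visual reading with no threshold. A reader might infer that a floor effect endangers the primary conclusion. The simulated one-sided error of 0.027 to 0.029 against 0.025 does not support that, within its limits: unadjusted, a single time point, and assumed floors of 12% to 42%.

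**What to change.** Replace the sentence in SAP section 13.5, through the amendment log in section 14, with one executable analysis on the PEM-point scale. Either of these would do; name one.

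- Refit the primary mixed model with robust standard errors clustered by site.
- Fit a fractional logit (binomial family, logit link, PEM/100) to the six-month score, with the primary covariates and site-clustered robust standard errors, and standardise to a difference in mean PEM points.

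In both cases report the six-month difference with its 95% CI and say how it will be read against the 7-point margin. State the trigger, or run the analysis regardless. An ordinal model (`ologit` or `meologit`) may be added, labelled supportive only.

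First reconcile Appendix A with sections 7.1, 9 and 13.2 on the direction of PEM, the bound used, and six versus seven points. Until then no analysis can be read against the margin without ambiguity.

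Avoid a bootstrap that resamples within arm-by-site cells. With 310 participants at up to 40 sites the average cell holds 310/80 = 3.9, or 248/80 = 3.1 after attrition. Resampling cells of size n understates variance by about 1/n, here roughly 26% to 32%, which favours non-inferiority.

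The cost is one amended sentence and a short model run. No new data are needed.

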13.7.2 Missing Data

Mixed-effect models assume that data is missing at random (MAR) and uses the correlation of withinsubject observations to adjust for any missing outcome data. Therefore, participants will be included in the primary analysis model if they have completed the PEM Hand Health Profile for at least one follow-up timepoint and they have data for all baseline covariates within the model.

If the overall proportion of participants not included within the primary model, due to missing outcome data at all time points or missing baseline covariates, is greater than 5%, the impact of missing data on the primary analysis will be assessed using multiple imputation by chained equations. The imputation model will include key baseline variables (age, sex, digital nerve injury, anaesthetic type, baseline PEM Hand Health Profile score and baseline EQ5D-5L score).

A 'burn –in' of 150 will be used and 50 imputed datasets will be created. The primary analysis will then be rerun within the imputed datasets and Rubin's rules will be used to combine the multiply imputed estimates.

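### The primary model leaves out randomised participants who have follow-up PEM scores but lack a baseline covariate: an avoidable, modest loss of precision that a simple rule for missing baseline PEM would prevent

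*SAP*

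**What the plan says.** SAP 13.5 fits a covariance pattern mixed model to PEM at six weeks, three months and six months. It adjusts for digital nerve injury, anaesthetic type and two baseline PEM scores (pre- and post-injury). On who enters the model it says "Participants will only be included in the model if they have complete data for the baseline covariates" and at least one valid follow-up score. SAP 13.7.2 repeats the condition: participants enter if, besides a follow-up score, "they have data for all baseline covariates within the model".

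Under SAP 7.1 a PEM profile "will not be scored if more than two items are missing"; with one or two of the 11 items missing, the mean of the others is substituted.

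SAP 13.7.2 provides multiple imputation by chained equations (50 datasets) if more than 5% of participants are outside the primary model. Missing baseline covariates and missing outcome at every time point are counted together. The imputed analysis sits among the sensitivity analyses.

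On principle, SAP 13.2 says "Analyses will follow the principles of intention-to-treat (ITT") and qualifies this by the availability of data. Protocol 5.5.4 promises an intention-to-treat primary analysis by randomised group and sets no complete-covariate condition.

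**The concern.** The rule lets a missing covariate remove an observed primary outcome. A participant may return all three follow-up questionnaires and still contribute nothing to the primary estimate because one of two baseline questionnaires had three blank items. The SAP gives no reason for this. The provision in 13.7.2 does not undo it: at or below 5% nothing is imputed, and above 5% the primary estimate still omits these patients.

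At stake are some precision in a trial planned at exactly 90% power, and an analysis set that depends on baseline completeness as well as on randomisation and follow-up.

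**Working it through.** **Inputs.** SAP section 9 (Sample Size): "For 90% power and alpha=0.025, 310 participants are required", "within a margin of seven points on the PEM", and a "95% two-sided confidence interval (equivalent to a one-sided 97.5% CI) and 20% attrition". The SD is 17; Protocol 5.5.2 writes "SD=17; upper 80% confidence limit (22"). Allocation is 1:1. The proportion with a missing baseline covariate is not given, so a range is assumed.

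**Reproducing 310.** With a true difference of zero,

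n per arm = 2 × (1.960 + 1.282)² × 17² / 7² = 123.9, rounded up to 124.

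This gives 248 evaluable, and 248 / 0.80 = 310, an exact match. The figure rests on SD 17; SD 22 would need 416 evaluable and 520 in total.

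**Power after further exclusions.** For a fraction f of the 248 excluded on top of attrition,

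power = Φ(7 / (17 × √(2/n)) − 1.96), with n = 124 × (1 − f).

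| f | Evaluable | Power |
|---|---|---|
| 0 | 248 | 90.0% |
| 3% | 241 | 89.1% |
| 5% | 236 | 88.5% |
| 10% | 223 | 86.8% |

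**What the 5% trigger permits.** The trigger is a share of all randomised: 0.05 × 310 = 15.5, so up to 15 can be left out without imputation. If all 15 were otherwise evaluable, 248 − 15 = 233 remain and power is 88.2%, a loss of about 1.9 points. That is the extreme case, because it requires that nobody lacks follow-up PEM at every time point; such patients use up the same 5%. The 10% row corresponds to about 25 patients, or 25 / 310 = 8%, and would already trigger imputation.

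**Bias and the proposed handling.** Simulation used 4,000 trials per setting, 248 patients, a true difference of zero, and analysis of covariance at a single time point. Baseline was missing either completely at random or depending on the baseline value, but never on arm. Complete-case analysis and overall-mean substitution of the missing baseline were compared, with baseline–outcome correlation 0, 0.3 or 0.5.

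- Mean error was at most 0.06 PEM points for either method, which is within simulation noise.
- Mean substitution gained about 0.2 to 1.7 points of power at 5% missing, and 1.5 to 3 points at 10% missing.

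**The case against.** The strongest reply is that this is a transparent choice with safeguards. SAP 13.2 limits intention-to-treat to available data, and everyone retained is analysed as randomised. Baseline PEM is collected before randomisation, so excluding on it does not by itself distort the comparison. Missing scores should be uncommon: baseline is collected at site (Protocol 5.1 and Table 5) and up to two blank items are tolerated. SAP 13.4 shows baseline data both as randomised and as analysed, so selection would be visible. Imputation is pre-specified with missing covariates named as a cause.

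Most of this stands, and it rules out three stronger readings that a reader might infer.

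- **That the rule biases the result or abandons intention-to-treat.** The documents do not show this. The simulation found no bias when missingness was unrelated to arm. What is departed from is the aim of including every randomised patient with outcome data.
- **That dropping patients costs more information than adjustment returns.** The documents give no baseline–outcome correlation r. Adjustment removes roughly r² of the variance, so it outweighs a 5% loss once r exceeds √0.05 ≈ 0.22, and a 10% loss above √0.10 ≈ 0.32. At an assumed r of 0.3 with 5% excluded, complete-case adjusted power is about 91%.
- **That the tabulated power loss is expected.** It is an upper bound from an unadjusted, single-time-point formula, with exclusions placed on top of the 20% allowance.

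The reply does not explain why the loss should be accepted. Adjustment and full inclusion are compatible, so the value of adjusting is no argument for excluding.

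**Conclusion.** The point holds as one of efficiency and completeness. As written, the primary estimate omits randomised participants with observed PEM because a covariate is missing, and imputation never replaces that estimate.

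The cost is modest: at worst about 2 points of power below the 5% trigger, 3.2 points (90.0% to 86.8%) if 10% of the evaluable patients were lost, and none if exclusions fall within the attrition allowance. These sizes rest on SD 17, margin 7, a true difference of zero and assumed missingness.

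The absence of bias rests on missingness being unrelated to arm. That is secure for baseline PEM. It is less certain for digital nerve injury and anaesthetic type, which SAP 7.3.3 lists among the primary surgery details and which come from a setting where the operating team knows the allocation (SAP section 11).

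**What to change.** Replace the inclusion sentence in SAP 13.5, and its repeat in 13.7.2, along these lines:

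- All randomised participants with at least one valid post-randomisation PEM score are included in the primary model.
- A missing pre- or post-injury baseline PEM is replaced by the overall mean of that score, ignoring arm and outcome, optionally with a missing indicator.
- For digital nerve injury and anaesthetic type, values are recovered from source records where possible; otherwise a missing category is used. Missingness of these two is reported by arm. The surgery form alone is not enough as the source, since it is where they are recorded in the first place.
- Multiple imputation stays as a sensitivity analysis.

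Two related places should be reconciled in the same edit. SAP Table 1 attaches the pre- and post-injury footnote to PRWHE and EQ-5D-5L, whereas SAP 7.1 and Protocol Table 5 attach it to PEM. The imputation model in 13.7.2 names a single baseline PEM score although the primary model uses two. Both bear on which missing scores exclude a patient.

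The cost is a short SAP amendment and a few lines of code, with no new outcome data; recovering surgery details means some source-record checks. The amendment should be made before outcomes are examined by arm.
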